Official Title: Oxygen Reserve Index (ORi)
Validation of INVSENSOR00014

Date of Protocol: May 14, 2018

NCT Number: NCT03500341

Oxygen Reserve Index (ORi) Validation of INVSENSOR00014

Protocol/Test Procedure Title	Oxygen Reserve Index (ORi) Validation of INVSENSOR00014
Lead Investigator	[name], MS, BS Senior Manager, Clinical Research/Laboratory Masimo Corporation [name]
Other Investigators	[REDACTED]
Expected Start Date	Based on IRB Approval Certification Approval Date
Expected End Date	Based on IRB Approval Certification Expiration Date
IRB	E&I West Coast Board – IRB00007807
Date Submitted To IRB	

Protocol Test Abstract:

The objective of this study is to validate the performance of Oxygen Reserve Index (ORi) as computed by the Masimo device in healthy volunteers. The changes in ORi measurements are compared to changes in PaO₂ values obtained from arterial blood samples analyzed by a laboratory CO-oximeter reference instrument.

APPROVALS

Author	Date	Engineering	Date
Quality Assurance	Date	Manufacturing	Date

Oxygen Reserve Index (ORi) Validation of INVSENSOR00014

STATEMENT OF COMPLIANCE

This document is a protocol for a clinical research study sponsored by Masimo Corporation. The study will be conducted in compliance with all stipulations of this protocol, the conditions of IRB approval, 21 CFR Part 50, 21 CFR Part 56, 21 CFR Part 812, ISO-14155, and International Conference on Harmonization E6 Good Clinical Practice (ICH GCP).

The protocol, informed consent form(s), recruitment materials, and all participant materials will be submitted to the Institutional Review Board (IRB) for review and approval. Approval of both the protocol and the consent form must be obtained before any participant is enrolled. Any amendment to the protocol will require review and approval by the IRB before the changes are implemented to the study.

1. PURPOSE

This test procedure describes the method used to validate the performance of Oxygen Reserve Index (ORi) as measured by the Masimo INVSENSOR00014 sensors connected to the Masimo Radical-7 pulse oximeter and Masimo Root monitor in healthy volunteers. The changes in ORi measurements are compared to changes in PaO₂ values obtained from arterial blood samples analyzed by a laboratory CO-oximeter reference instrument.

Outcome Measure:

This study reports ORi specificity, sensitivity and concordance for Masimo's ORi measurement system as compared to PaO₂ from blood samples.

2. BACKGROUND

Masimo Corporation develops non-invasive medical technologies. These devices have applications in the operating room, critical care unit, emergency room, emergency transport vehicles, as well as physician's offices.

[figure not shown]
An invasive blood sample analyzed by a CO-oximeter reference instrument gives the best measure of arterial oxygen concentration as well as other blood solutes, but cannot measure these parameters continuously and requires skin puncture, arterial line placement and subsequent risk of infection, hematoma, and other physiological damage. Masimo SET and Masimo Rainbow technologies allow real-time, non-invasive monitoring of oxygen saturation (and other blood solutes) and has the potential to improve clinical outcomes while reducing the cost of care and risks to both patients and clinicians associated with arterial and venous punctures.

2.1. Technology Background

Pulse oximetry is governed by the following principles:

- Oxyhemoglobin (oxygenated blood) and deoxyhemoglobin (non-oxygenated blood) differ in their absorption of red and infrared light (spectrophotometry).
- The amount of arterial blood in tissue changes with arterial pulses (photoplethysmography). Therefore, the amount of light absorbed by the varying quantities of arterial blood changes as well.
- The CO-Oximeter utilizes a sensor with various light-emitting diodes (LEDs) that pass light through the site to a photodiode (detector). See figure below.

Oxygen Reserve Index (ORi) Validation of INVSENSOR00014

1. Light Emitting Diodes (LEDs)
(2+ wavelengths)
2. Detector

- Signal data is obtained by passing various visible and infrared lights through a capillary bed (for example, a fingertip, a hand, a foot) and measuring changes in light absorption during the blood pulsatile cycle. The maximum radiant power of the strongest light is limited to $\leq 25\text{mW}$. The detector receives the light, converts it into an electronic signal and sends it to the Masimo hardware (e.g. Rad-57, Radical-7) for calculation. Once the oximeter receives the signal from the sensor, it utilizes Masimo SET signal extraction technology for calculation of the patient's functional oxygen saturation, pulse rate and other blood parameters.

2.2. Parameter Background

A continuous supply of oxygen is essential for normal cell function. Failure of a patient's oxygen supply to meet metabolic needs is common to all forms of circulatory failure, tissue acidosis, and ultimately mortality. Like all essential commodities for body functions, optimal quantities of oxygen are required. A patient's oxygen status can be largely classified into 3 ranges: Hypoxia (less than normal), Normoxia (normal) and Hyperoxia (more than normal). The three states are typically classified using dissolved oxygen levels in the plasma (PaO_2), instead of arterial hemoglobin oxygen saturation (SaO_2), due to sensitivity of PaO_2 in all three states including hyperoxia (unlike SaO_2). Figure I.¹ shows the three oxygen states based on PaO_2 values along with the relationship between PaO_2 and SpO_2 (which is a proxy for SaO_2)

OxyHemoglobin Dissociation Curve

[figure not shown]

Figure 1: The oxygen dissociation curve with the three oxygen states

¹ Martin, L. (1999). *All you really need to know to interpret arterial blood gases*, Page 73, Lippincott Williams & Wilkins.

Oxygen Reserve Index (ORi) Validation of INVSENSOR00014

In order to prevent episodes of hypoxia, patients in critical care are administered a certain amount of surplus oxygen to prevent hypoxia even when oxygen supply may be lost intermittently. However this excess supply should be in moderation as large amounts of oxygen may result in potential lung damage. Hence it becomes imperative to monitor the amount of surplus oxygen in blood.²

Currently, in order for clinicians to monitor a patient's oxygen status, both continuously and non-invasively, they utilize a pulse oximeter to obtain SpO₂ (a proxy for SaO₂) levels. However, SpO₂ is sensitive in the normoxic and hypoxic regions and largely remains flat in the hyperoxic region (Figure 1) clinicians generally resort to invasive blood draws to obtain PaO₂ values which provide oxygen status within the hyperoxic zone. This method has multiple drawbacks such as intermittent samples to potential delay between time of blood draw to the time when the PaO₂ value is obtained through blood gas machines.

The ORi Parameter may help provide clinicians with a convenient noninvasive method for reference information in regards to PaO₂. While not a direct measurement of PaO₂, ORi provides a continuous and non-invasive index which correlates with changes in PaO₂ values (in the range of 100 to 200mmHg).

2.3 Investigational Study Devices

The investigational devices to be used in this study are the Masimo INVSENSOR00014 rainbow disposable sensor, Masimo Radical-7 Pulse CO-Oximeter, and Masimo Root Patient Monitoring and Connectivity Platform. [REDACTED]

INVSENSOR00014 is similar to existing FDA cleared Masimo rainbow disposable sensors. [REDACTED]

Investigational sensor is equivalent to the FDA cleared sensors with regard to intended use on the surface of the skin, the choice of materials, biocompatibility, manufacturing process and risk of exposure to the subject to any energy or light source. They do not pose any additional risk to patients as compared to the FDA cleared sensors.

The Masimo Root Patient Monitoring Platform is an FDA-cleared patient monitoring and connectivity platform that offers rainbow® and Masimo SET® measurements with other parameters in an integrated platform. With docking capabilities for the Radical-7® handheld monitor and multiple networking/connectivity options, Root integrates multiple streams of data into one display monitor. The Masimo Radical-7 pulse oximeter is an FDA-cleared noninvasive monitoring platform featuring Masimo SET Measure-through Motion and Low Perfusion™ pulse oximetry with the option to measure multiple additional blood constituents and physiologic parameters. [REDACTED]

**Oxygen Reserve Index (ORi) Validation of
INVSENSOR00014**

² D. S. Martin and M. P. W. Grocott III. , Oxygen therapy in anaesthesia: the yin and yang of O₂ Br. J. Anaesth. (2013) 111 (6): 867-871 doi:10.1093/bja/aet291

² Habre W1, Peták F2. Perioperative use of oxygen: variabilities across age. Br J Anaesth. 2014 Dec;113 Suppl 2:ii26-ii36. doi: 10.1093/bja/aeu380

3. REFERENCE

Consent To Be A Research Subject Oxygen Reserve Index (ORi) Validation of INVSENSOR00014

Post Care Instructions

Oxygen Reserve Index (ORi) Validation of INVSENSOR00014 Case Report Form (CRF)

Oxygen Reserve Index (ORi) Validation of INVSENSOR00014 Healthy Volunteers Needed

Advertisement

Oxygen Reserve Index (ORi) Validation of INVSENSOR00014 Recruitment Script

Health Assessment Questionnaire Health Assessment Questionnaire Oxygen Reserve Index

(ORi) Validation of INVSENSOR00014

Confidentiality Agreement

Volunteer payment form

Informed Consent Process

Clinical Study Request Form (CSRF)

5. STUDY POPULATION

5.1. Inclusion Criteria

- Subject is 18-50 years of age.
- Subject weighs a minimum of 110 lbs and no more than 250 lbs unless subject is over 6 feet tall.
- Hemoglobin value is greater than or equal to 11 g/dL.
- Baseline heart rate \geq 45 bpm and \leq 85 bpm.
- CO value \leq 2.0% FCOHb
- Subject has a physical status of ASA I or II (American Society of Anesthesiology Class 1; Healthy subjects without any systemic disease at all. American Society of Anesthesiology Class II; subjects with mild systemic disease) as it applies to the systemic disease portion of the classification.
- Systolic Blood Pressure \leq 140 mmHg and Diastolic Blood Pressure \leq 90 mmHg.
- Subject is able to read and communicate in English and understands the study and risks involved.

5.2. Exclusion Criteria

- Subject is pregnant.
- Subject smokes (smoking includes e-cigarette use)
- Subject has a BMI $>$ 35 and has been classified as morbidly obese or at an increased risk for participation by a medical professional.
- Subject has open wounds, inflamed tattoos or piercings or any visible healing wounds.
- Subject experiences frequent or severe headaches and/or migraine headaches.
- Subject has known drug or alcohol abuse or uses recreational drugs.
- Subject has experienced a concussion or head injury with loss of consciousness within the last year.
- Subject has any chronic bleeding disorders (i.e. hemophilia)
- Subject has any history of a stroke, myocardial infarction, seizures or heart attack.
- Subject has any cancer or history of cancer (not including skin cancer).
- Subject has a chronic neurological disease (i.e. multiple sclerosis, Huntington's disease).
- Subject has any cardiac dysrhythmia(s) (i.e. atrial fibrillation) and has not received clearance from their physician to participate.
- Subject has known neurological and/or psychiatric disorder (i.e. schizophrenia, bipolar disorder) that interferes with the subjects' level of consciousness.
- Subject has any medical condition which in the judgment of the investigator and/or medical staff, renders them ineligible for participation in this study (Discretion of investigator).
- Subject has Wolff-Parkinson-White Syndrome or Stokes - Adams syndrome.
- Subject who has taken anticoagulant medications within the last 30 days.
- Subject has taken opioid pain medication within 24 hours of start of study.
- Subject has either signs or history of peripheral ischemia or carpal tunnel syndrome.
- Subject has had invasive surgery within the past year- including but not limited to major dental surgery, gallbladder, heart, appendix, major fracture repairs (involving plates/ screws), jaw surgery, urinary tract surgery, plastic surgery, major ENT surgery, joint replacement or gynecological surgeries, heart surgery or thoracic surgery.
- Subject has donated blood within the last 2 weeks.
- Subject has symptoms of congestion, head colds, flu or other illnesses.
- Subject experiences claustrophobia or has generalized anxiety disorder.

Oxygen Reserve Index (ORi) Validation of INVSENSOR00014

- Subject has been in severe car accident(s) or a similar type of accident(s) requiring hospitalization within the last 12 months.
- Subject has had a concussion within the past 12 months.
- Subject has chronic unresolved asthma, lung disease or respiratory disease.
- Subject is allergic to lidocaine, latex, adhesives, or plastic.
- Subject has heart conditions, insulin-dependent Diabetes or uncontrolled hypertension.
- Subject has given vaginal delivery, had a pregnancy terminated, a miscarriage with hospitalization, or had a C-section within the past 6 months.
- Subject intends to participate in any heavy lifting, repetitive movement of their wrist (including riding a motorcycle) or exercise (working out, riding a bike, riding a skate board etc.), or any activity that will put additional stress on the wrist within 24 hours of the study.
- Discretion of investigator/study staff.

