7.4. PROCEDURES

- 7.4.1. Standard hospital-type monitors will be placed on the subject, including ECG, blood pressure, and a reference pulse oximeter for safety monitoring by medical staff.
- 7.4.2. Proprietary Masimo data collection software will be used to verify all oximeters are reading. If not, proper sensor positioning will be checked and sensors may be repositioned, as needed.
- 7.4.3. Rainbow parameter output values (e.g., SpO₂, pulse rate, PI) along with ORi will be recorded using the proprietary Masimo data collection software. These values match the values calculated by the instrument at runtime.
- 7.4.4. A peripheral venous line will be placed in the subject's hand or arm. This line may be used for the qualifying venous blood draw and for safety or clinical intervention required during the study.
- 7.4.5. Local anesthetics such as lidocaine, ethyl chloride spray, or Pain Ease skin refrigerant spray may be used in the event that an IV is placed to numb the site. Subjects will be given the option to have lidocaine or numbing spray be used during IV placement for the purpose of making catheter placement more comfortable for the subjects.
- 7.4.6. After intravenous access is established, one or more intra-arterial catheter(s) (arterial line or A-line) will be placed in the radial artery of the subject's wrist. The A-line is placed to facilitate continuous blood pressure measurement for subject safety monitoring, and/or to enable repeated removal of blood aliquots for reference arterial blood gases (ABG), Hgb, Hct, as well as other non-infectious blood solutes.
- 7.4.7. After arterial access is established, sensors will be placed on the required sensor sites.

Arterial blood samples will be drawn at specified targeted increments.

**Oxygen Reserve Index (ORi) Validation of
INVSENSOR00014**

Upon indication the subject is comfortable, a gas mixture will be administered. The proportion of inspired oxygen (FiO₂) will be increased in specified targeted increments

7.4.9 After reaching the desired targeted FiO₂ levels during hyper-saturation, the proportion of inspired oxygen (FiO₂) will be decreased in specified targeted increments until reaching room air; samples should be drawn at each targeted saturation level. After reaching room air, the subject may be allowed to breathe room air

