11. SUPPORTING DOCUMENTATION AND OPERATIONAL CONSIDERATIONS

**Oxygen Reserve Index (ORi) Validation of
INVSENSOR00014****11.1 Measures Taken to Protect the Rights and Welfare of Subjects**

- 11.1.1 All subjects will be monitored closely throughout the study. There will be an ACLS certified medical doctor present in the study area throughout the study.
- 11.1.2 The following measures will be taken to ensure the confidentiality of the subjects:
 - 11.1.2.1 A code (identification) number for each subject will be kept on file.
 - 11.1.2.2 Only their corresponding identification number will identify subjects.
 - 11.1.2.3 Access to identifying documents (IC, SSN, photo ID) and data will only be made to the principal investigators in the study and study staff.
 - 11.1.2.4 The confidentiality and retention of these documents will be protected to the extent provided and required by the law.

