draws will be performed by qualified personnel. An ACLS certified physician will be in attendance throughout the entire procedure, and the study will be completed under their general supervision. Other anticipated adverse events that may occur, include but are not limited to: vasovagal (passing out/fainting), infection to the skin or area right below the skin, lightheadedness, feeling flush/ warm, feeling nauseated, throwing up, seizures, sudden drop in blood pressure/ sudden increase in blood pressure, sudden drop in heart rate/ sudden increase in heart rate, tingling sensation of face/arms and/or sweating, and mouth dryness. These anticipated adverse events are expected to be temporary.

- 13.6. Risk From Oxygen Administration: There are no risks associated with high oxygen/oxygen administration for less than 24 hours as long as subjects do not have any cardiac conditions, COPD or any other lung diseases. Subjects' answers on the health questionnaire will help the medical staff decide if they can safely participate in this study; subjects are encouraged to let the study staff know if they have any concerns.
- 13.7. Low Oxygen Concentration Risks: Risks associated with hypoxia include dizziness, shortness of breath, drowsiness, or headache. If or when this occurs, the study can be stopped. There is an extremely small risk of loss of consciousness, damage to vital organs, or death from lack of oxygen. The study shall be stopped by the subject or clinical staff long before this could occur. Other anticipated adverse events that may occur, include but are not limited to: vasovagal (passing out/fainting), lightheadedness, feeling nauseated, throwing up, seizures, sudden drop in blood pressure/sudden increase in blood pressure, sudden drop in heart rate/sudden increase in heart rate, tingling sensation of face, arms and/or legs, sweating, mouth dryness. These anticipated adverse events are expected to be temporary.

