- 13.12. Lidocaine (injection) Risks: Insertion of the Lidocaine may be discomforting and can feel like a slight pinch along with a warm/burning sensation. Other anticipated adverse events that may occur, include but are not limited to: Flushing or redness of the skin, itching skin, small red or purple spots on the skin, unusually warm skin, bruising, bleeding at the application site, and swelling. These adverse events are expected to be temporary.
- 13.13. Although not common, it is also possible to have an allergic reaction to injectable lidocaine. Subjects should not take part in this study if they are allergic to lidocaine injection or other types of numbing medicine, or if they have a heart rhythm disorder such as Wolff-Parkinson-White Syndrome or Stokes-Adams syndrome. Subjects are instructed to tell the study staff right away if they experience hives; difficulty breathing; swelling of your face, lips, tongue or throat.
- 13.14. Ethyl Chloride (Lidocaine Spray): Ethyl Chloride is a topical anesthetic which is used to prevent pain by cooling the skin. Although unlikely, the anticipated adverse events that may occur, include but are not limited to: changes in skin color (i.e. Flushing or redness of the skin), delayed wound healing, rash, itching and swelling. These adverse events are expected to be temporary.

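### The dysrhythmia exclusion in 5.2 exempts subjects cleared by their own physician, which fits poorly with the unqualified heart-conditions exclusion and with 13.13 (minor eligibility-consistency point)

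*Combined protocol and SAP*

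**What the plan says.** Four places in the combined protocol and SAP bear on a volunteer with a rhythm disorder.

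- **5.2, dysrhythmia item:** "Subject has any cardiac dysrhythmia(s) (i.e. atrial fibrillation) and has not received clearance from their physician to participate". Both parts must be true for the item to exclude.
- **5.2, later in the same list:** "Subject has heart conditions, insulin-dependent Diabetes or uncontrolled hypertension". Nothing qualifies heart conditions by severity or clearance, and the term is not defined.
- **13.13, within the lidocaine risks:** subjects should not take part if allergic to numbing medicine, "or if they have a heart rhythm disorder such as Wolff-Parkinson-White Syndrome or Stokes-Adams syndrome". There is no clearance exception. A separate 5.2 item already excludes the two named syndromes unconditionally.
- **13.6, oxygen administration:** the statement that oxygen for under 24 hours carries no risk holds "as long as subjects do not have any cardiac conditions, COPD or any other lung diseases".

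Section 7.3.4 adds that anyone who does not meet the inclusion and exclusion criteria is ineligible. Section 5.1 sets a baseline heart rate of 45 to 85 bpm and requires ASA class I or II.

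**The concern.** A screener with a physician-cleared case of atrial fibrillation, the protocol's own example, gets different signals from different lines. The dysrhythmia item lets the subject through, the heart-conditions item appears to stop them, and 13.13 appears to say they should not take part. The protocol does not say whether a dysrhythmia is a heart condition, so two screeners could decide differently.

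What is at stake is subject safety and uniform eligibility. Section 7.4 raises inspired oxygen in steps, returns the subject to room air and then desaturates them. Section 13.7 acknowledges an extremely small risk of loss of consciousness, organ damage or death from lack of oxygen, and 13.1 says the subject gains no benefit. The clause also relies on the subject's own physician. The consent and screening steps in 7.3 do not describe collecting or reviewing a clearance, or telling that physician what the procedure involves.

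**Working it through.** No arithmetic applies, and the plan has no figure to reproduce. The check is to take one case, a subject with atrial fibrillation and their own physician's clearance, through each provision.

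| Provision | Type | Result for the cleared subject |
|---|---|---|
| 5.2 dysrhythmia item | Eligibility rule | Does not exclude |
| 5.2 heart-conditions item | Eligibility rule | Excludes, if a dysrhythmia is a heart condition |
| 5.2 item on the two named syndromes | Eligibility rule | Does not apply to atrial fibrillation |
| 13.13 | Instruction within risk text | Should not take part, if 'such as' introduces examples; silent, if only the two syndromes are meant |
| 13.6 | Risk statement | No-risk statement does not cover the subject |
| 7.3.4 | How criteria combine | Passing one item does not waive another |

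**Reading A: a dysrhythmia is a heart condition.** Under 7.3.4 one failed criterion is enough, so the heart-conditions item excludes the subject. The clearance clause then changes no decision, yet it still tells the screener that an exemption exists.

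**Reading B: a dysrhythmia is not a heart condition for 5.2.** This is arguable, because the list gives dysrhythmia, myocardial infarction and the two syndromes their own items, which could leave heart conditions as a residual category. The clearance clause then decides the matter, and the subject may enter unless staff use their discretion.

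- If 13.13 is read broadly, entry goes against its plain wording.
- If 13.13 is read narrowly, it does not conflict with entry.
- On either reading of 13.13, the subject falls outside the 13.6 no-risk statement. The residual-category argument comes from the structure of the 5.2 list and does not carry over to 13.6, which refers to any cardiac condition.

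**With the clearance clause deleted,** the dysrhythmia item excludes the subject on both readings. It then agrees with the heart-conditions item and with either reading of 13.13, and 13.6 no longer leaves this subject uncovered.

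**Check on the deletion.** Without the clause, the item covers any dysrhythmia, with no severity limit. Section 5.1 admits resting rates down to 45 bpm. If a screener treated a slow but permitted rate as a rhythm disorder (an assumption; the protocol does not define dysrhythmia), the shortened item would exclude people whom 5.1 accepts. The deletion therefore needs a clarifying phrase.

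**The case against.** The strongest case against is that nothing in the plan truly conflicts. Under 7.3.4 the criteria apply together, so on reading A the clause is merely redundant. On reading B there is no conflict within 5.2, and a cleared subject enters by design. Section 13.6 describes risk and does not decide who may enrol. Section 13.13 belongs to the lidocaine text, its two named syndromes are already excluded, and local anaesthetic for IV placement is optional under 7.4.5.

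There are also safeguards. Staff may exclude anyone at their discretion. 5.2 also bars this group: "Subject who has taken anticoagulant medications within the last 30 days". ASA class is limited to I or II. Section 13.6 says subjects' "answers on the health questionnaire will help the medical staff decide if they can safely participate in this study". Section 7.4.1 provides that "Standard hospital-type monitors will be placed on the subject, including ECG, blood pressure", and 11.1.1 that "There will be an ACLS certified medical doctor present in the study area throughout the study". The health questionnaire and case report form listed in section 3 are not available here and may settle the question in practice.

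Much of this stands. The point about 7.3.4 is right, and so is the one about 13.6. The 13.13 conflict is the weaker of the two, although 'such as' ordinarily introduces examples. The safeguards reduce exposure, but none says whether a cleared dysrhythmia is eligible; monitoring and physician attendance manage risk only after entry.

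A reader might infer that the protocol plainly admits people with atrial fibrillation, or that 13.6 and 13.13 formally prohibit what 5.2 permits. The documents support neither. Admission depends on how heart conditions is read, 13.6 is not an eligibility rule, and 13.13 has a narrower possible meaning.

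**Conclusion.** The inconsistency is real but minor. The clearance clause either has no effect or admits a cleared subject whom the risk section does not cover and whom 13.13, on its plain reading, advises against taking part. Which of these applies depends on an undefined term.

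No size can be attached. The documents give no frequency of cleared dysrhythmia, and none is assumed. On reading A no such subject enters; on reading B one could, subject to the safeguards. It should not be inferred that the ORi results are affected: nothing in the documents links this clause to sensitivity, specificity or concordance, and the target of 22 completed subjects is unchanged. The conclusion rests on the published text alone, without the questionnaire or case report form.

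**What to change.** In the 5.2 dysrhythmia item, delete the second condition (the clause on physician clearance), so that any cardiac dysrhythmia excludes. In the same item, state that a resting heart rate within the 45 to 85 bpm range of 5.1 is not by itself a dysrhythmia. The heart-conditions item, 13.6 and 13.13 can stay as they are.

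The cost is IRB review under section 16 and possibly a few more screen failures, because volunteers with a benign, cleared dysrhythmia could no longer enrol on any reading.

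Keeping the clearance route is a legitimate alternative. It would need an exception in the heart-conditions item, a risk statement in 13.6 for cleared subjects and, unless 13.13 is taken to mean only the two named syndromes, narrower wording there.

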7.3. CONSENTING AND SCREENING

- 7.3.1. Study staff will discuss the informed consent process and the study with the potential subjects. The subjects will be provided with enough time to read and understand the informed consent document and their questions will be answered by study staff prior to the subject signing the informed consent form. No study related activities will be conducted until consent is signed.
- 7.3.2. The subject's weight and height are self-reported, however the subject may be weighed on a scale for verification.
- 7.3.3. Subjects will be asked to provide a copy of their valid government photo ID and/or Social Security Number (SSN) card to verify subject identity. The copies of these forms of identification will be stored along with the subject's consent. The confidentiality and retention of these documents will be protected to the extent provided and required by law.
- 7.3.4. Subjects will be asked a brief series of health questions to ensure their eligibility for this study. Subjects who do not meet the inclusion and exclusion criteria will not be eligible to participate in the study.
- 7.3.5. Subject demographic information including age, sex, skin tone, ethnicity, height and weight will be collected. These may be recorded for data analysis and/or subject safety monitoring purposes.
- 7.3.6. In addition, a medical history will be recorded after the initial screening questionnaire.
- 7.3.7. Pre-procedure vital signs will be recorded for subject safety monitoring. Spikes in blood pressure and heart rate can be expected during line placement, needle sticks, blood draws etc. and may also be attributed to anxiety/nervousness relating to a new environment. Only the initial recorded blood pressure and/or heart rate determines a subject's qualification for the study.
- 7.3.8. Female subjects will be required to take a pregnancy test. Results will be noted in study documentation. If the pregnancy test is positive, the subject will be notified and removed from the study.

**Oxygen Reserve Index (ORi) Validation of
INVSENSOR00014**

- 7.3.9. A venous sample will be obtained via needle stick or by placement of an IV and analyzed to verify that the subject meets the inclusion criteria for hemoglobin level and HbCO. The subject will be excluded from the study if the values from the blood draw fall outside the ranges stated in the inclusion criteria.
- 7.3.10. Subjects may have a blanket placed on them for their comfort.

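### The allergy exclusion in section 5.2 names lidocaine as its only numbing agent, while section 13.13 advises against participation for allergy to any numbing medicine, so the two eligibility rules need reconciling (minor)

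*Combined protocol and SAP*

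**What the plan says.** Five places in the combined protocol and SAP bear on this.

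- **Section 5.2 (Exclusion Criteria)** has one allergy item: "Subject is allergic to lidocaine, latex, adhesives, or plastic". Lidocaine is the only numbing agent in it.
- **Section 7.3.4 (Consenting and Screening)** says what decides eligibility: "Subjects who do not meet the inclusion and exclusion criteria will not be eligible to participate in the study". It does not refer to section 13.
- **Section 7.4.5 (Procedures)** names the agents: "Local anesthetics such as lidocaine, ethyl chloride spray, or Pain Ease skin refrigerant spray may be used". Use is the volunteer's choice: "Subjects will be given the option to have lidocaine or numbing spray be used during IV placement".
- **Section 13.13 (Risks and Benefits)** states its own participation rule: "Subjects should not take part in this study if they are allergic to lidocaine injection or other types of numbing medicine". The same sentence goes on to heart rhythm disorders and names Wolff-Parkinson-White and Stokes-Adams syndromes.
- **Section 13.14 (Risks and Benefits)** opens with "Ethyl Chloride (Lidocaine Spray): Ethyl Chloride is a topical anesthetic which is used to prevent pain by cooling the skin".

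**The concern.** Sections 5.2 and 13.13 answer the same question differently: which known allergies to numbing medicine should keep a volunteer out? Section 5.2 stops at lidocaine, and 13.13 goes on to other numbing medicines. The list that decides eligibility is the narrower of the two, and 7.4.5 permits agents from the group that only 13.13 covers.

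What is at stake is consistent protection of healthy volunteers, who under 13.1 get no benefit from taking part. Two staff members who each follow the protocol could reach opposite decisions about the same person. No endpoint, analysis or sample size depends on it.

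**Working it through.** No arithmetic applies, and the plan gives no figure to reproduce on this point. The check sets the passages side by side.

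**Step 1. Do the sprays count as numbing medicines in the protocol's own terms?** Yes. Section 7.4.5 lists both sprays under local anesthetics, and 13.14 says that "Ethyl Chloride is a topical anesthetic which is used to prevent pain by cooling the skin". The list in 7.4.5 is given as examples, so further agents are not ruled out.

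**Step 2. How does each rule treat each agent?**

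| Known allergy to | Allowed by 7.4.5 | Named in 5.2 | Within 13.13 |
|---|---|---|---|
| Lidocaine | Yes | Yes | Yes |
| Ethyl chloride spray | Yes | Unclear | Yes |
| Pain Ease spray | Yes | No | Yes |
| Another numbing agent | Not excluded | No | Yes |

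The ethyl chloride row is unclear because 13.14 puts a lidocaine label on it, while 7.4.5 treats lidocaine and ethyl chloride as different agents. If the label governs, lidocaine in 5.2 may be meant to include ethyl chloride, and one of the three named agents (Pain Ease) is outside 5.2. If 7.4.5 governs, two of the three are outside. The mismatch exists on both readings.

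**Step 3. Follow one person through.** Take a volunteer with a known allergy to Pain Ease.

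1. No specific item in 5.2 applies, so the listed criteria can be met.
2. Under 7.3.4, those criteria decide eligibility.
3. Under 13.13, this person should not take part.
4. Under 7.4.5, this person could be offered a numbing spray at IV placement and may decline it.

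Items 2 and 3 conflict whether or not an agent is used, because 13.13 concerns participation and not use of the agent.

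**Step 4. Is the narrower wording deliberate?** No reason is given. Lidocaine and the two syndromes named in the same sentence of 13.13 all appear in 5.2. That suggests the remaining allergy phrase was left out by oversight. It is an inference only: 5.2 and 13.13 were not matched word for word elsewhere either, since 5.2 leaves room for other dysrhythmias with a physician's clearance.

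**The case against.** The strongest reply is that screening is more than the list in 5.2. Section 7.3.4 calls for health questions, 7.3.6 for a medical history, and section 3 cites a Health Assessment Questionnaire. Section 5.2 also has two discretion items, one of them for any medical condition that staff judge to make a person ineligible. A numbing agent is optional, so a person who knows of an allergy can decline. An ACLS-certified physician is present and a crash cart is on site.

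Most of this stands, and it limits the consequence. It does not remove the conflict: once such an allergy is disclosed, 5.2 and 13.13 still point to different decisions, and neither discretion item names allergy or requires exclusion.

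A reader might infer more than the documents support:

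- **That such a person passes screening and nobody asks.** The questionnaire is not in the documents and may well ask. All that can be shown is that the listed criteria can be met.
- **That 13.13 is an absolute bar.** Its wording is that such subjects should not take part.
- **That the sprays carry a risk of breathing difficulty or throat swelling.** Those symptoms follow the sentence in 13.13 about allergy to injectable lidocaine, which 5.2 already excludes. For ethyl chloride, 13.14 lists skin changes, delayed wound healing, rash, itching and swelling, calls them unlikely and expects them to be temporary.
- **That two of the three named agents are definitely uncovered.** That count depends on how the 13.14 heading is read.

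**Conclusion.** The point holds as a minor internal inconsistency in eligibility. Sections 5.2 and 13.13 state different participation rules for allergy to numbing agents, and 7.3.4 relies on the narrower one. Following 5.2 as written can admit a person whom 13.13 says should stay out, and 7.4.5 then allows that person to be offered such an agent.

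It affects at least Pain Ease, and ethyl chloride as well if 7.4.5 rather than the 13.14 heading is followed. The documents give no allergy frequency. That the number affected is very small is an assumption, though a reasonable one for a study needing 22 completed subjects. The specificity, sensitivity and concordance analysis is unaffected.

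The conclusion rests on reading the sprays as numbing medicines, which 7.4.5 and 13.14 support, and on taking 7.3.4 at its word that the listed criteria decide eligibility. It does not rest on what the questionnaire or consent form says, since neither is available.

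**What to change.** 1. Reconcile 5.2, 7.4.5 and 13.13 so that one allergy rule applies throughout. Which rule that is, and whether the change falls in 5.2, in 13.13 or in the agents allowed, is for the sponsor's medical staff.
2. Confirm that the Health Assessment Questionnaire matches that rule. It may already do so.
3. Resolve the 13.14 heading against 7.4.5, so that a reader can tell whether ethyl chloride and lidocaine are the same item or two.

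The cost is a few words in the protocol, possibly one line in the questionnaire, and the IRB review that section 16 requires for any modification. At most there would be a rare extra screen failure. Because section 9 counts completed subjects, that would cost one more recruitment and no data.
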